8.6 Multiple Assessments

When clinical assessments or lab samples are inadvertently taken or analyzed multiple times, this produces multiple measures for the same date (and time in the case of labs) for the same subject. In such cases, the average of such multiple assessments for labs or vitals will be used for this time point for this subject. For immunogenicity, ANA, dsDNA and the efficacy assessments, the least favorable value will be used.

8.7 Safety Data Conventions

Safety data will be handled according to the BMS safety data convention standards³ and Supplement to Safety Guidelines for abatacept⁴.

9 CONTENT OF REPORTS

The results of this study will be presented in a standard BMS Clinical Study Report (CSR).

CSR Primary analysis Month 6:

At the time of the primary analysis (i.e. after all subjects complete the Double-Blind Period), the final efficacy and safety analysis up to Day 169 will be provided (Double-Blind Period). In addition, all available safety data will be summarized for the cumulative abatacept period up to Year 1 (interim analysis). No efficacy analysis beyond Day 169 will be provided.

CSR Year 1:

This CSR will include the final analysis for Year 1 (efficacy and safety).

APPENDIX 1 DOCUMENT HISTORY

Table 9-1: Document History

Version	Statistician	Date	Notes/Revisions
1.0	[REDACTED]	13 September 2017	Original version
2.0	[REDACTED]	10 August 2018	
 • Subgroup analyses by stimulated salivary flow at screening and/or baseline < 0.1 (subgroup 1) and ≥ 0.1 (subgroup 2) will only be provided if there are at least 10 patients in each treatment group for both subgroups. • Subgroup analyses for mean change from baseline for ESSDAI at day 169 (by gender, race, region, ...) will only be provided if at least 10 subjects in each treatment group (instead of 10% currently in SAP v1.0). ESSDAI-by-time interaction removed from model. • Sensitivity analysis including the efficacy data after 42 days (post treatment up to day 169): only provided 
 - if at Day 169 there are at least 10% of subjects with missing data in either treatment group for the primary analysis - and on top, at Day 169 there are at least 10% more non-missing measurement in either treatment groups using all collected data (including post treatment) compared to number of non-missing measurement in primary analysis • Sensitivity analysis for MAR (tipping point and control-based pattern imputation): only if at Day 169 there are at least 10% of subjects with missing data in either treatment group for primary analysis • Forest plot: for treatment difference instead of by treatment group • Change wording ‘clinically important change’ to ‘clinically important improvement’. • Replacement of worst eye by study eye (and none study eye) • According to SAP v1.0 the minimal detectable change for 4 binary exploratory variables (stimulated and unstimulated salivary flow, Schirmer’s test, ocular staining score and tear break-up time) will be explored to define a meaningful change in each endpoint. Implementation in SAP v2.0: Proportion of subjects with 25% improvement and proportion of subjects with 50% improvement • Added: proportion of subject with ESSDAI < 5 up at Day 169

Table 9-1: Document History

Version	Statistician	Date	Notes/Revisions
			
 • Added: proportion of subjects with ESSPRI < 5 up at Day 169 • Back-up models for minimal risk weight macro: 
 - The back-up model 1: exclude the japan and salivary flow stratification variables. - The back-up model 2: exclude all stratification variables. • Back-up for proc MI (sensitivity analysis): 
 - The back-up model 1: exclude the Japan and salivary flow stratification variables. - The back-up model 2: exclude all stratification variables. • Tear Break Up Time: In case only 2 measurements are available, the average of the 2 measurements will be calculated. In case there is only 1 measurement, that measurement will be used for the analysis. • Shift tables for ESSDAI components added • Proportion of improvement and proportion of worsening for ESSDAI components added • No longitudinal analysis for ESSDAI components in case changes from baseline = 0 for all subjects for all timepoints.

APPENDIX 2 RELEVANT PROTOCOL DEVIATIONS

- Eligibility Deviations:
 - Subjects who did not meet 2016 ACR/EULAR classification criteria at screening
 - Subjects with ESSDAI < 5 at screening
 - Subjects who were anti-SSA/Ro negative at screening
 - Subjects who have received IV, IM, SC or intra-articular corticosteroids within 4 weeks of first double-blind abatacept dose
 - Subjects who have taken MTX within 12 weeks of first double-blind abatacept dose
 - For subjects on hydroxychloroquine at first date of double-blind abatacept dose: subjects on hydroxychloroquine for < 12 weeks and/or the dose not stable for at least 4 weeks prior to Day 1
- Incorrect dosing:
 - Subjects received treatment different than randomized group
 - If more than 4 consecutive doses are missed just prior to the primary time point, Day 169
- Restricted and Prohibited medications:
 - Subjects receiving a single IM, IV, SC or oral course of high dose of corticosteroid (> 10mg/day for > 1 consecutive days) in the Double-Blind Treatment Period within 56 days of primary time point (i.e. the efficacy assessment done at Day 169).
 - Subjects receiving a non-biologic DMARD (except hydroxychloroquine already taken at Day 1) at any time during the Double-Blind Treatment Period up to the day prior to the efficacy assessment done at Day 169
 - Subjects receiving a biologic DMARD at any time during the Double-Blind Treatment Period up to the day prior to the efficacy assessment done at Day 169
 - Subjects adding hydroxychloroquine during the Double-Blind Treatment Period up to the day prior to the efficacy assessment done at Day 169 while not on this medication at Day 1.

Note: Day 169 is the time point used for the **primary analysis** of ESSDAI at Day 169.

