Women of childbearing potential (WOCBP) is defined as any female who has experienced menarche and who has not undergone surgical sterilization (hysterectomy or bilateral oophorectomy) and is not postmenopausal. Menopause is defined as 12 months of amenorrhea in a woman over age 45 years in the absence of other biological or physiological causes. In addition, females under the age of 55 years must have a serum follicle stimulating hormone, (FSH) level > 40 mIU/mL to confirm menopause.

*Females treated with hormone replacement therapy, (HRT) are likely to have artificially suppressed FSH levels and may require a washout period in order to obtain a physiologic FSH level. The duration of the washout period is a function of the type of HRT used. The duration of the washout period below are suggested guidelines and the investigators should use their judgement in checking serum FSH levels.

- 1 week minimum for vaginal hormonal products (rings, creams, gels)
- 4 week minimum for transdermal products
- 8 week minimum for oral products

Other parenteral products may require washout periods as long as 6 months. If the serum FSH level is > 40 mIU/mL at any time during the washout period, the woman can be considered postmenopausal.

Double-blind Period

Subjects are permitted to continue oral corticosteroids at doses of less than or equal to prednisone 10 mg daily (or equivalent) provided that the dose is stable for at least 4 weeks prior to randomization and remains stable throughout the double-blind period. During the double-blind period, decrease in dose or discontinuation of oral corticosteroids is permitted only for adverse events or intolerance. IM, IV, SC and intra-articular corticosteroids are not permitted. Topical corticosteroids are permitted throughout the study.

Open-label Period

During the open-label period, oral corticosteroids at a dose of prednisone, up to 10 mg daily, or equivalent, may be initiated. The dose of oral corticosteroids may be decreased for any reason, but the dose may not be increased above prednisone 10 mg daily (or equivalent). Intra-articular corticosteroids are permitted, but IM, IV and SC corticosteroids are not permitted. Topical corticosteroids are permitted throughout the study.

Analgesics and NSAIDs:

- NSAIDs and analgesics (including topical NSAIDs) are not permitted within 12 hours before a joint assessment

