6.3 Populations for Analyses

- Modified Intent-to-treat (ITT) analysis population: all randomized subjects who receive at least one dose of study medication. This population will exclude subjects who are randomized, but not treated. Given the blinded nature of this study, it is reasonable to assume that subjects who discontinue prior to the receipt of study medication do so for reasons unrelated to study medication and that excluding these patients will not bias the estimate of the treatment effect. Moreover, in previous studies, it happened very infrequently that subjects were randomized and not treated. Analyses using the Modified ITT analysis population will group the subjects according to the treatment group to which they are randomized. All efficacy analyses will use the Modified ITT population
- Intent-to-treat (ITT) analysis population: all randomized subjects. This population will also include randomized subjects who are never treated. Subjects who were randomized and never treated and did not return for any assessments after discontinuation (i.e. lost to follow-up or withdrew consent) will be excluded from the ITT analysis population. This population will be used for a sensitivity analysis of the primary and key secondary endpoints. Details are provided in [Section 7.1](#). Analyses using the ITT analysis population will group the subjects according to the treatment group to which they are randomized.
- Per-protocol (PP) analysis population: all randomized subjects who receive at least one dose of study medication, excluding the subjects with relevant protocol deviations. Analyses using the PP analysis population will group the subjects according to the treatment group to which they are randomized.
- As-treated analysis population: all subjects who receive at least one dose of study medication. Analyses using the as treated analysis population will group the subjects on an as-randomized basis unless the subject received the incorrect medication for the entire Double-Blind Period. In that case, the subject will be analyzed in the treatment group associated with the incorrect medication they received (“as-treated”). This population will be used for the safety analyses.
- Open-Label population: all randomized subjects who receive at least one dose of abatacept during the open-label period.

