7.2 Study Conduct

Relevant protocol deviations, which could have an impact on the primary endpoint, will be identified for all subjects who are randomized and receive study medication during the Double-Blind Period. Details of relevant protocol deviations are provided in [APPENDIX 2](#).

All subjects with relevant protocol deviations that could affect the primary efficacy will be identified prior to database lock and unblinding of treatment assignment. All relevant protocol deviations will be listed and summarized by treatment group. The subjects identified with relevant protocol deviation will not be excluded from any analysis population described in [Section 6.3](#). If at least 10% of the subjects in one of the treatment arms in the modified ITT analysis population demonstrate relevant protocol deviations, a per-protocol analysis will be performed for the primary endpoint, change from baseline in ESSDAI at Day 169. The per-protocol analysis will exclude data from subjects with relevant protocol deviations as specified in [APPENDIX 2](#).

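### Three of the twelve per-protocol deviation items are timed to an abatacept dose that placebo subjects never receive, the on-study steroid item drops the intra-articular route, and SAP 7.2 contradicts 6.3; all can be fixed by wording before unblinding

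*SAP*

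**What the plan says.** SAP Appendix 2 has six eligibility deviations, two dosing deviations and four on-study medication deviations. Three of the eligibility items use an abatacept dose as their reference date:

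- steroids: "Subjects who have received IV, IM, SC or intra-articular corticosteroids within 4 weeks of first double-blind abatacept dose"
- methotrexate: "Subjects who have taken MTX within 12 weeks of first double-blind abatacept dose"
- hydroxychloroquine: "For subjects on hydroxychloroquine at first date of double-blind abatacept dose", after which the same item counts dose stability back from Day 1.

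The on-study steroid item begins "Subjects receiving a single IM, IV, SC or oral course of high dose of corticosteroid". It applies above 10 mg/day for more than one consecutive day, within 56 days of the Day 169 assessment. The protocol's double-blind corticosteroid rules (printed after Section 3.3.3 in the file) state "IM, IV, SC and intra-articular corticosteroids are not permitted". They allow low-dose oral steroid "provided that the dose is stable for at least 4 weeks prior to randomization and remains stable throughout the double-blind period".

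SAP 6.3 defines the per-protocol population as "all randomized subjects who receive at least one dose of study medication, excluding the subjects with relevant protocol deviations". SAP 7.2 says "The subjects identified with relevant protocol deviation will not be excluded from any analysis population described in" Section 6.3, and then says the per-protocol analysis leaves out data from those same subjects. That analysis covers ESSDAI at Day 169 only. It runs when deviators reach 10% of an arm (7.2) or exceed 10% of an arm (7.5.1).

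**The concern.** A rule that removes subjects from a randomized comparison should be applicable in both arms as written. If the three items are programmed literally, a placebo subject who had methotrexate or an injected steroid shortly before Day 1 stays in the per-protocol set, while an abatacept subject with the same history is removed. The count that triggers the analysis would be distorted in the same way.

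The steroid item has a different fault. The SAP treats an intra-articular injection as relevant before the first dose, but not in the 56 days before the primary assessment, and gives no reason. ESSDAI has an articular domain, so a subject injected close to Day 169 would remain in the set meant to exclude such treatment.

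Finally, 7.2 and 6.3 cannot both be followed. Two statisticians working from the SAP could build different per-protocol sets.

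**Working it through.** **Reference date.** SAP 7.4.1 sets the first abatacept injection at the first double-blind abatacept treatment for subjects randomized to abatacept, and at the first open-label treatment for subjects randomized to placebo. A first double-blind abatacept dose therefore exists in one arm only. Protocol 3.3.2 times the same steroid and methotrexate exclusions to randomization (Day 1), which exists in both arms. SAP 8.2 defines baseline by the first dose of double-blind study medication, also arm-neutral. The other nine Appendix 2 items refer to screening, dosing, the double-blind period or Day 169, and are arm-neutral.

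**Steroid routes.**

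- Eligibility item: IV, IM, SC, intra-articular.
- Protocol, not permitted in the double-blind period: IM, IV, SC, intra-articular.
- On-study item: IM, IV, SC, oral above 10 mg/day. Intra-articular is the one injected route missing.

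**Trigger.** 10% of 86 is 8.6, so the smallest qualifying count is 9 under either wording. The wordings differ only when an arm size is a multiple of 10: with 80 per arm, 8 against 9; with 90 per arm, 9 against 10.

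**Power.** The plan's figure reproduces. With n = 86 per arm, difference 3, SD 4.8 and two-sided alpha 0.05: 3 / (4.8 × √(2/86)) = 4.098, and Φ(4.098 − 1.960) = 98.4%. The exact t calculation gives 98.3%, against 98% stated. If 10% to 20% of each arm were excluded (an assumption; 77 to 69 left), t-test power would be 97.1% to 95.4%. Loss of power is not the issue.

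**Size of a literal reading (illustration).** The documents give no deviation rates. Assume that a proportion e = 2% to 6% of each arm have one of the three abatacept-timed deviations and a further b = 3% to 7% have another deviation.

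- Extra exclusions from the abatacept arm: 86 × e, which is 86 × 0.02 = 1.7 up to 86 × 0.06 = 5.2 subjects on average.
- Chance that the analysis is triggered, with 9 or more in either arm and independent arms: the literal reading gives 1 − (1 − P[Bin(86, b+e) ≥ 9]) × (1 − P[Bin(86, b) ≥ 9]). A neutral anchor gives 1 − (1 − P[Bin(86, b+e) ≥ 9])².

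| b | e | literal | neutral |
|---|---|---|---|
| 3% | 2% | 2.9% | 5.5% |
| 3% | 6% | 37.0% | 60.2% |
| 5% | 4% | 38.7% | 60.2% |
| 7% | 6% | 83.1% | 96.1% |

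The literal reading makes the per-protocol analysis less likely to run and, when it runs, takes more subjects from one arm.

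**The case against.** The strongest reply is that one-arm exclusion will not happen. SAP 7.2 has deviations identified for all randomized and treated subjects, before database lock and unblinding. Blinded reviewers cannot know who received abatacept, so the only usable date is the first blinded injection. That stands: the anchor is a wording error, and a reader who infers a demonstrated bias between arms goes further than the documents allow. It is still a rule that misfires if programmed as written.

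Second, the protocol on file runs to Amendment 01, while the SAP was written after Amendments 6 and 8, both of which touched the corticosteroid rules (SAP 2.4). The intra-articular text may have changed. This also stands, so that part has to be checked against the current protocol. The anchor and the conflict between 7.2 and 6.3 rest on the SAP alone.

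Third, 7.2 limits relevant deviations to those that could affect the primary endpoint, so the list is selective by design. Oral steroid started or raised to 10 mg/day or less, and hydroxychloroquine increases in existing users, fall outside it. A reader might call these omissions errors, but they can equally be a judgement of relevance. The protocol's bar on new oral steroid is also implied by its stable-dose rule and not stated outright. They call for reconciliation or a reason.

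Fourth, the sentence in 7.2 is loose but the intent is recoverable, because 7.2 goes on to exclude deviators from the per-protocol analysis. That is fair, and it makes the correction easy.

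**Conclusion.** The point holds as a set of SAP wording faults: three items without a reference date in the placebo arm, one injected route missing from the on-study steroid item, and a contradiction between 7.2 and 6.3. The two trigger wordings differ on paper but give the same count, 9, at the planned 86 per arm.

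The consequence is limited. The per-protocol analysis is conditional, supportive and for ESSDAI only; the modified ITT primary analysis does not use Appendix 2.

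Two larger inferences are not supported. The articular domain runs from 0 to 6 (SAP Table 8.1.1-1), and one might set 6 points against the 3-point design difference. But 6 is the most a single subject can change, and one such subject moves an 86-subject arm mean by 6/86 = 0.07 points. A bias would also need unequal frequency between arms, and no frequencies are given. Nor can the per-protocol analysis be called the only check on background treatment: SAP 7.3.4 points to a Section 7.4.4 on medications of special interest, and the text after 7.4.3 is blacked out.

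The verdict assumes arms near 86 and, for the intra-articular point, that the current protocol still has the rule shown in the file.

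**What to change.** Before unblinding, amend the SAP text:

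1. In the three Appendix 2 items, replace the abatacept dose with the first dose of double-blind study medication (as in SAP 8.2) or with Day 1, using one anchor throughout.
2. Check the on-study steroid item against the current amended protocol. If intra-articular use is still not permitted in the double-blind period, add that route.
3. Reconcile the on-study oral steroid and hydroxychloroquine items with the stable-dose rules, or state why smaller changes are not treated as relevant. Any new hydroxychloroquine wording should keep the existing item, which counts adding the drug at any time in the double-blind period.
4. In 7.2, say that subjects with relevant deviations are excluded from the per-protocol population only.
5. Use one trigger wording in 7.2 and 7.5.1.

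The cost is a text revision. The per-protocol set may become slightly smaller; on the illustration above, even 20% exclusion leaves power near 95%.

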APPENDIX 3 REGIONS

Table 9-2: Regions

Regions by Country	
North America	USA/Puerto Rico
	Canada
South America	Argentina
	Brazil
	Mexico
Europe	Czech Republic
	France
	Germany
	Italy
	Sweden
Asia	Japan
	Korea
ROW (Rest of World)	Australia
